5.2 APPENDIX 2 CHANGES TO PROTOCOL-PLANNED ANALYSES

Regarding the calculation of z-scores for physical growth (recumbent length/height, weight, head circumference) the protocol referred to Center for Disease Control (CDC) Growth Charts. However, the CDC website recommended the World Health Organization (WHO) growth charts for children <24 months of age. If possible, we will incorporate this recommendation. In addition, percentiles of these measurements will be calculated as well.

It was planned to use longitudinal repeated measures modeling to analyze trends in key growth and development parameters over time; however, as out of the 12 patients enrolled 7 patients had withdrawn or died in less than 4 years, this analysis is not likely to be informative and will be omitted.

5.3 APPENDIX 3 DEMOGRAPHICS AND BASELINE CHARACTERISTICS, PRIOR OR CONCOMITANT MEDICATIONS

Demographics, baseline characteristics, medical/surgical history, alglucosidase alfa and Pompe disease history, and retrospective motor milestones

The following demographics and baseline characteristics, medical and surgical history, and disease characteristics at baseline will be summarized using descriptive statistics in the enrolled population.

Demographic and baseline characteristics:

- age (months) at signing of informed consent
- age group (Newborns [0-27 days], Infants and toddlers [28 days - 23 months], Children [2-11 years])
- age (months) at first alglucosidase alfa infusion*
- age (months) at Pompe diagnosis
- age (months) at first Pompe symptom
- time (months) from first Pompe symptom to first alglucosidase alfa infusion*
- time (months) from Pompe diagnosis to first alglucosidase alfa infusion*
- gender (Male, Female)
- race (American Indian or Alaska Native, Asian, Black, Native Hawaiian or Other Pacific Islander, White)
- ethnicity (Hispanic or Latino, not Hispanic or Latino)
- weight (kg, percentile) at treatment baseline
- recumbent length/height (cm, percentile) at treatment baseline
- BMI (kg/m²)

- head circumference (cm, percentile) at treatment baseline
- CRIM status

*Note that patients may have received alglucosidase alfa prior to entering the study.

Baseline safety and efficacy parameters (apart from those listed above) will be presented along with the safety and efficacy summaries.

Medical/surgical history (excluding those reported as part of the Pompe medical history) includes medical history according to body systems (infectious disease, allergic, metabolic/endocrine/nutritional, hematopoietic, musculoskeletal, dermatologic, HEENT, breasts, respiratory, cardiovascular, gastrointestinal/hepatic, genitourinary/renal, neurologic, psychiatric/psychosocial). No coding will be done for medical/surgical history.

Alglucosidase alfa and Pompe disease history include the following:

- date of first symptoms of Pompe disease
- date of diagnosis of Pompe disease
- date of first alglucosidase alfa infusion
- eyes, ears, nose, and throat (enlarged tongue, chronic otitis media, tympanic membrane tube(s) placed, hearing loss, visual screening ever performed)
- respiratory (currently receiving ventilatory support, tracheostomy ever performed, pneumonia, sleep disturbances/apnea)
- cardiovascular (congestive heart failure, evidence of left ventricular hypertrophy, evidence of cardiac involvement [cardiomegaly], evidence of cardiac arrhythmia prior to receiving alglucosidase alfa)
- gastrointestinal and renal (hepatomegaly, failure to thrive, feeding difficulties, gastroesophageal reflux, currently fed by mouth, currently on nutritional support, renal insufficiency)
- musculoskeletal hypotonia, muscle weakness in upper extremities, muscle weakness in lower extremities, delayed motor milestones, regression of motor milestones, joint contractures)

Retrospective motor milestones assessed include the following (yes/no/unknown; if yes, date first noted):

- Holds head up
- Bear weight on legs
- Rolls
- Sits with support
- Sits without support
- Pulls to stand

- Walks with support
- Walks without support
- Runs
- Walks up steps
- Walks down steps

Prior or concomitant medications and therapies

All medications will be coded using the World Health Organization-Drug Dictionary (WHO-DD) using the version in effect at Sanofi at the time of database lock.

- Prior medications and therapies (eg, tube feeds) are those the patient used prior to first IMP administration in the study (ie, alglucosidase alfa received prior to study entry will be counted as prior medication). Prior medications can be discontinued before first study administration or can be ongoing during the treatment period.
- Concomitant medications and therapies are any interventions received by the patient concomitantly to the IMP during the on-treatment period.
- A given medication can be classified as a prior medication and/or as a concomitant medication. If it cannot be determined whether a given medication was taken prior or concomitantly, it will be considered as both prior and concomitant medication.

The prior and concomitant medications will be summarized for the enrolled and exposed population by anatomic and therapeutic level. The summaries will be sorted by decreasing frequency of anatomic category (ATC) based on incidence. In case of equal frequency, alphabetical order will be used. Patients will be counted once in each ATC category (anatomic or therapeutic) linked to the medication.

5.4 APPENDIX 4 DATA HANDLING CONVENTIONS

5.4.1 Derivations

The following formulas will be used for computation of parameters:

Age (months) at signing of informed consent = (date of informed consent - date of birth + 1)/30.4375

Age (months) at first alglucosidase alfa infusion = (date of first infusion - date of birth + 1)/30.4375

Age (months) at Pompe diagnosis = (date of Pompe diagnosis - date of birth + 1)/30.4375

Age (months) at first Pompe symptom = (date at first Pompe symptom - date of birth + 1)/30.4375

Time (months) from first Pompe symptom to first alglucosidase alfa infusion = (date at first infusion - date at first Pompe symptom + 1)/30.4375

Time (months) from Pompe diagnosis to first alglucosidase alfa infusion = (date at first infusion - date at Pompe diagnosis + 1)/30.4375

BMI = weight [kilograms] /(height [meters])²

Computation of Z-scores (standardized age and gender adjusted values) and percentiles for height/length, weight, and head circumference will be according to Center for Disease Control (CDC) growth Charts(1) and World Health Organization (WHO) growth charts(2). The WHO growth charts are recommended for children <24 months of age.

5.4.2 Handling of lab data

Handling of potentially clinically significant abnormalities

For PCSAs with 2 conditions, one based on a change from baseline value or a normal range and the other on a threshold value, with the first condition being missing, the PCSA will be based only on the second condition.

For a PCSA defined on a threshold and/or a normal range, this PCSA will be derived using this threshold if the normal range is missing; eg, for eosinophils the PCSA is >0.5 GIGA/L or > ULN if ULN \geq 0.5 GIGA/L. When ULN is missing, the value 0.5 should be used.

Measurements flagged as invalid by the laboratory will not be summarized or taken into account in the computation of PCSA values.

Handling of ADA titer with missing or non-numerical values

If the ADA titer is reported as “<value”, then the limit value will be used for summary tables. For example, if a value is reported as “<100”, 100 will be used for the data point in the calculation of the summary statistics. The respective listings will however still report the original data, eg, <100. No imputation will be performed for missing values.

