4.7.3 Additional safety assessments

4.7.3.1 Laboratory variables, vital signs, physical examinations (PE), and electrocardiograms (ECGs)

The following laboratory variables, vital signs, physical examinations (PE), and electrocardiogram (ECG) variables will be analyzed.

- Hematology:
 - Complete blood count with differential
- Clinical chemistry:
 - Metabolism: glucose, total protein, albumin, creatine kinase (CK), creatine kinase MB (creatine kinase muscle, brain isoform [CK-MB]), creatine kinase MB/total creatine kinase
 - Electrolytes: sodium, potassium, chloride, calcium, phosphorus, bicarbonate
 - Renal function: creatinine, blood urea nitrogen (BUN), uric acid (urate)
 - Liver function: alanine aminotransferase (ALT) [serum glutamic pyruvic transaminase (SGPT)], aspartate aminotransferase (AST) [serum glutamic oxaloacetic transaminase (SGOT)], alkaline phosphatase, total bilirubin

- Urinalysis:
 - Urinalysis for quantitative analysis: urine appearance, specific gravity, pH, protein, glucose, ketones, bilirubin, and blood.
 - Microscopy will be performed if clinically indicated.
- Vital signs: heart rate, systolic and diastolic blood pressure, respiratory rate, and temperature
- PE body systems: General Appearance, Skin, HEENT, Lymph Nodes, Heart, Lungs, Breasts, Abdomen, External Genitalia, Pelvic, Rectal, Extremities/Joints, Neurological, Mental Status examinations
- 12-lead ECG variables:
 - Intervals and measurements: heart rate, RR, PR, QRS duration, QRS axis, QT, QTc (Bazett and Fridericia correction)
 - Findings: sinus rhythm, LVH, RVH, conduction abnormalities

For summary tables, data below the lower limit of quantitation/detection limit (LLOQ) will be replaced by half of the LLOQ, while data above the upper limit of quantification (ULOQ) will be replaced by ULOQ value.

Analyses of quantitative variables

For all laboratory variables and quantitative ECG variables (intervals and measurements) above, descriptive statistics for results and changes from baseline will be provided for each planned visit during the on-treatment period. Vital signs data will be provided in a listing.

PE findings

PE findings (normal, abnormal, not examined) for each body system will be presented in a listing.

Analyses of ECG findings

For ECG, the incidence of patients with at least one abnormal ECG during the treatment-emergent period will be summarized according to the following baseline status categories:

- Normal/missing
- Abnormal

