4.8 OTHER ANALYSES

4.8.1 *Immunogenicity analyses*

Anti-rhGAA IgG Binding Antibody

Participant's ADA status, response variable, and kinetics of ADA responses (see definitions below) will be summarized for all patients with available ADA data.

Kinetics of ADA response

Kinetics of ADA response will be derived for patients ever ADA positive, whether with ADA already present at baseline or seroconverted during the study. Time to ADA onset (seroconversion) and time from seroconversion to first peak titer will be described with mean, SD, median, Q1, Q3, minimum, and maximum statistics.

- **Persistent ADA response** is defined as ADA positive at the last sample timepoint and meets one of the following two criteria:
 - ADA positive at two or more sampling time points post baseline, where the first and the last ADA-positive post-baseline samples (irrespective of any negative sample in between) are separated by at least 16 weeks; or
 - ADA positive at last two sampling time points, irrespective of the time in between.
- **High ADA response** is a subcategory of persistent ADA response and identifies a patient who was persistently seropositive positive, had a peak titer ≥ 12800 , and was seropositive at final assessment.
- **Tolerized ADA response** is a subcategory of persistent ADA response and identifies a patient who was persistently seropositive, but seronegative at the final assessment.

The following definitions will also be used:

- **ADA peak titer** (highest ADA titer from first study infusion of alglucosidase alfa) for ever positive patients.
- **Time to ADA seroconversion from first alglucosidase alfa infusion in study**

Time to seroconversion (days) from 1st alglucosidase alfa infusion in study will be calculated by (date of seroconversion - date of 1st alglucosidase alfa infusion in study + 1)

- **Time to first alglucosidase alfa ADA peak titer from seroconversion**

Time to first peak titer (weeks) from seroconversion will be calculated by (date of first peak titer - date of seroconversion + 1) / 7

- **ADA peak titer category** (always negative, 100-800, 1600-6400, ≥ 12800).
- **Last ADA titer** (final assessment after first study infusion of alglucosidase alfa) for ever positive patients.
- **ADA last titer category** (≤ 800 , 1600-6400, ≥ 12800).

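### The last-titer classes for ADA give no row to patients who have become seronegative, and entering <100 as 100 blurs negative and lowest positive in the summary statistics

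*SAP*

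**What the plan says.** SAP 4.8.1 (Immunogenicity analyses) uses two class schemes for titers.

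- **Peak titer:** "always negative, 100-800, 1600-6400", with a top class of ≥12800. Negatives have their own class and the lowest positive class starts at 100.
- **Last titer:** the "ADA last titer category" has three levels, ≤800, 1600-6400 and ≥12800. The last titer is taken at the "final assessment after first study infusion of alglucosidase alfa) for ever positive patients", so the sample may be negative although the patient was positive before.

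The same section summarises titers by geometric mean, geometric SD, median, quartiles, minimum and maximum, and by class, and plans titer plots for individual patients.

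SAP 5.4.2 sets the substitution rule: if a titer is reported as less than a value, "then the limit value will be used for summary tables". In its example of a result reported as <100, "100 will be used for the data point in the calculation of the summary statistics". It then says: "The respective listings will however still report the original data, eg, <100".

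SAP 4.8.1 also defines response types. Persistent response "is defined as ADA positive at the last sample timepoint and meets one of the following two criteria". Tolerized response is a subcategory of persistent response, for patients who are negative at the end.

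**The concern.** In a study followed for ten years, a last-titer table is where a reader would look to see how many antibody-positive patients still have antibody at the end. As specified, that table has no row for those who do not. A patient with no detectable antibody and a patient still at 800 give the same entry.

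The substitution rule adds to this on the numerical side. A result below 100 and a result of exactly 100 become the same number in the geometric mean, the quartiles and the minimum. If any sample is below 100, the printed minimum is 100, which reads as a positive titer.

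Anti-rhGAA IgG formation is listed among the secondary safety endpoints (SAP Table 2), so these tables will be read.

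**Working it through.** **1. Apply the SAP's own rule.** A result of <100 becomes 100, as in the SAP's example. Passing results through the substitution and the last-titer classes gives:

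| Reported | Value in statistics | Last-titer class |
|---|---|---|
| <100 | 100 | ≤800 |
| 100 | 100 | ≤800 |
| 800 | 800 | ≤800 |
| 1600 | 1600 | 1600-6400 |
| 12800 | 12800 | ≥12800 |

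The first two rows are identical in both output columns.

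**2. Size of the shift in the geometric mean.** Let f be the share of <100 values in a summary. Replacing them with 100 instead of 50 multiplies the geometric mean by (100/50)^f = 2^f. The documents do not give f, so these shares are assumptions, written as counts out of 12 (the number enrolled, SAP 5.2):

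| Number <100, of 12 | f | 2^f |
|---|---|---|
| 1 | 0.083 | 1.06 |
| 3 | 0.25 | 1.19 |
| 6 | 0.50 | 1.41 |
| 9 | 0.75 | 1.68 |
| 12 | 1.00 | 2.00 |

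The ceiling is a factor of 2, one doubling dilution. The median does not move while fewer than half of the values are <100. Peak titer is unaffected in any patient with a positive sample after the first study infusion, because the maximum is then at least 100 without any substitution.

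**3. Size of the shift in the last-titer table.** Moving one seronegative patient out of ≤800 changes that cell by 1/n, where n is the number ever positive. The documents do not give n. If all 12 enrolled patients were ever positive, 1/12 = 8.3 percentage points; if 8 were (assumed), 1/8 = 12.5 points.

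**4. Does the tolerized category show the loss instead?** Persistent response needs a positive last sample. Tolerized response needs a negative last sample and is a subset of persistent. No patient can meet both. As a check, all positive/negative sequences of 2 to 8 samples taken 13 weeks apart were enumerated. There are 4 + 8 + ... + 256 = 508. Of these, 247 are positive at some point and negative at the last sample, and none qualifies as tolerized under the text.

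A charitable reading would drop the last-sample condition from persistent response for this purpose. A patient positive only at Weeks 13 and 26 and negative afterwards would still be missed. The two positive samples are 26 − 13 = 13 weeks apart, short of the required 16, and they are not the last two samples.

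**The case against.** The strongest reply is that little depends on these tables. Safety analyses are descriptive, without testing (SAP 4.7). The antibody strata for TEAEs use high-response status, seroconversion status and peak class (SAP 4.7.2), not the last-titer class or an imputed mean. Listings keep <100, and each patient's titers are plotted over time. With 12 patients, those displays show loss of antibody directly. All of this stands. A reader might infer that the plan conceals loss of antibody altogether; the documents do not support that.

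A reader might also infer that the SAP contradicts itself, because in SAP 4.7.3.1 "data below the lower limit of quantitation/detection limit (LLOQ) will be replaced by half of the LLOQ". That rule belongs to a list of laboratory, vital-sign, physical-examination and ECG variables that does not include ADA, and ADA has its own explicit rule. The two rules differ, but that is not a contradiction. Half the limit is itself only a convention, so the factor 2^f compares two conventions and does not measure bias against a known truth.

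It can further be said that the peak scale needs a negative class because it can include never-positive patients, whereas the last-titer population is ever positive. That explains why an always-negative class is absent. It does not explain why there is no class for patients negative at the final sample.

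Finally, the SAP nowhere says that a negative sample is reported as <100. That is correct, and the part of the point about summary statistics is conditional on it.

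**Conclusion.** The point holds as a minor defect of presentation. The last-titer classes pool patients who are seronegative at the end with those still positive at 100-800. The tolerized category does not repair this, because as written no patient can enter it.

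The numerical part is smaller and conditional. If negatives are reported as <100, they cannot be told apart from the lowest positive titer in the summary statistics. Using the upper bound can only raise the geometric mean, by between 1 and 2 times against half-limit substitution. The actual factor depends on a share that the documents do not give.

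The effect stays within summary tables. Listings, individual plots and the antibody strata for TEAEs are untouched. The 8.3-point shift per patient should be quoted only with its condition that all 12 enrolled patients are ever positive.

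**What to change.** - **Last-titer classes:** negative, 100-800, 1600-6400, ≥12800, assigned from the positive/negative assay result and not from the substituted number.
- **Geometric means:** summarise titers among positive samples only and show the number of negative samples beside them. No substituted value is then needed. Replacing 100 with 50 would be only another convention and would leave the ≤800 cell as it is.
- **Response definitions:** reconcile persistent and tolerized so that the second can be met.
- **Reporting of negatives:** state in SAP 5.4.2 how a negative sample is recorded. SAP 4.8.1 refers to Section 5.4.1 for ADA handling, but the rule is in 5.4.2; correct the reference.

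No new data are needed. The cost is SAP wording, one output format and one more row in a table of at most 12 patients. The downside is that the cells become smaller still.

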5.4.3 Analysis windows for time points

The following analysis windows will decide how the scheduled and/or unscheduled visits will be used in the by-visit analyses of efficacy, safety, and exploratory variables.

A measurement (scheduled or unscheduled) will be used if it is available and measurement date is within the analysis window.

After applying these time windows, if multiple assessments are associated to the same time point, the closest from the targeted study day will be used. Except where specified otherwise, if the difference is a tie, the value after the targeted study day will be used. If multiple valid values exist within a same day, then all the valid values of the day will first be averaged before applying the

aforementioned rules. (Note that the rule of using the later date of the window does not conflict with any protocol-specified procedure that has to be done pre-infusion (eg, IgG assessments), as all IgG assessments will be performed prior to infusion unless there was a protocol deviation.)

If there is no measurement for a given parameter in an analysis window, data will be considered missing for the corresponding visit.

Efficacy assessments

The schedule for the efficacy assessments is shown in the following table.

Efficacy assessments	Schedule
Recumbent length/height, weight, and head circumference	Every 3 months age < 3 years; every 6 months 3 to <5 years, every 12 months \geq 5 years
Bayley-III	every 6 months ages 1 month to 42 months
Leiter-R/Leiter-3	from final Bayley-III assessment < 42 months of age, every 12 months
GMFM-88	every 6 months age < 5 years; every 12 months \geq 5 years
Pompe PEDI	every 6 months age < 5 years; every 12 months \geq 5 years

Given that patients enter study at different ages, if we define analysis windows for the efficacy endpoints based on the assessment schedule, the definitions will vary depending on each patient's age at study entry. In addition, due to the small patient population, we will focus on individual patient growth by age. The following analysis windows for efficacy assessments will not be used in by-visit summary tables or figures, but may be used in the patient listing to associate observations to the nearest study visits.

Maximum age at signing of the informed consent was 1.9 years.

Table 7 - Analysis window definition for recumbent length/height, weight, and head circumference

Scheduled visit post baseline	Targeted study day	Analysis window in study day
Screening/Baseline	-30 to -1	
Week 13	91	[46, 136]
Week 26	182	[137, 227]
Week 39	273	[228, 319]
Week 52	365	[320, 456]
Week 78	547	[457, 638]
Week 104	730	[639, 821]
Week 130	912	[822, 1003]
Week 156	1095	[1004, 1277]

Scheduled visit post baseline	Targeted study day	Analysis window in study day
Week 208	1460	[1278, 1642]
Week 260	1825	[1643, 2007]
Week 312	2190	[2008, 2372]
Week 364	2555	[2373, 2737]
Week 416	2920	[2738, 3102]
Week 468	3285	[3103, 3467]
Week 520	3650	[3468, 3650]

Study days are calculated considering Day 0 as the day of first administration of intervention.

Table 8 - Analysis window definition for Bayley-III and Leiter-R/Leiter-3

Scheduled Visit	Targeted study day	Analysis window in study day
Screening/Baseline	-30 to -1	
Week 26	182	[91, 273]
Week 52	365	[274, 547]
Week 104	730	[548, 912]
Week 156	1095	[913, 1277]
Week 208	1460	[1278, 1642]
Week 260	1825	[1643, 2007]
Week 312	2190	[2008, 2372]
Week 364	2555	[2373, 2737]
Week 416	2920	[2738, 3102]
Week 468	3285	[3103, 3467]
Week 520	3650	[3468, 3650]

Study days are calculated considering Day 0 as the day of first administration of intervention.

Table 9 - Analysis window definition for GMFM-88 and Pompe PEDI

Scheduled Visit	Targeted study day	Analysis window in study day
Screening/Baseline	-30 to -1	
Week 26	182	[91, 273]
Week 52	365	[274, 456]

Scheduled Visit	Targeted study day	Analysis window in study day
Week 78	547	[457, 638]
Week 104	730	[639, 821]
Week 130	912	[822, 1003]
Week 156	1095	[1004, 1277]
Week 208	1460	[1278, 1642]
Week 260	1825	[1643, 2007]
Week 312	2190	[2008, 2372]
Week 364	2555	[2373, 2737]
Week 416	2920	[2738, 3102]
Week 468	3285	[3103, 3467]
Week 520	3650	[3468, 3650]

Study days are calculated considering Day 0 as the day of first administration of intervention.

Safety and other exploratory assessments

Safety and other exploratory assessments are supposed to be conducted every 12 months with a window of \pm 60 days, except for Serum IgG collection and urine Hex4.

- Neuroimaging assessment
- Hearing testing
- Visual screening
- ECG
- Safety laboratory assessments
- Serum IgG collection (every 3 months to study month 24 and then every 12 months after that)
- Urine Hex4 (every 6 months to study month 24 and then every 12 months after that)

Table 10 - Analysis window definition for serum IgG visits

Scheduled Visit	Visit window defined in protocol (\pm 60 days)	Target study day	Analysis window in study day
Screening/Baseline	Day -30 to -1		-30 to -1
Week 13	Month 3	91	1 to 137
Week 26	Month 6	183	138 to 229
Week 39	Month 9	274	230 to 320
Week 52	Month 12	365	321 to 411
Week 65	Month 15	456	412 to 502
Week 78	Month 18	548	503 to 594

Scheduled Visit	Visit window defined in protocol (± 60 days)	Target study day	Analysis window in study day
Week 91	Month 21	639	595 to 685
Week 104	Month 24	731	686 to 914
Week 156	Month 36	1096	915 to 1279
Week 208	Month 48	1461	1280 to 1644
Week 260	Month 60	1826	1645 to 2009
Week 312	Month 72	2192	2010 to 2375
Week 364	Month 84	2557	2376 to 2740
Week 416	Month 96	2922	2741 to 3105
Week 468	Month 108	3287	3106 to 3470
Week 520	Month 120	3653	3471 to 3836

Study days are calculated considering Day 0 as the day of first administration of intervention.

Table 11 - Analysis window definition for urine Hex4

Scheduled Visit	Visit window defined in protocol (± 60 days)	Target study day for analysis windows	Range of study days for analysis window
Screening/Baseline	Day -30 to -1		-30 to -1
Week 26	Month 6	183	1 to 274
Week 52	Month 12	365	275 to 457
Week 78	Month 18	548	458 to 640
Week 104	Month 24	731	641 to 1096
Week 156	Month 36	1096	1097 to 1461
Week 208	Month 48	1461	1462 to 1826
Week 260	Month 60	1826	1827 to 2192
Week 312	Month 72	2192	2193 to 2557
Week 364	Month 84	2557	2558 to 2922
Week 416	Month 96	2922	2923 to 3287
Week 468	Month 108	3287	3288 to 3653
Week 520	Month 120	3653	3654 to 4018

Study days are calculated considering Day 0 as the day of first administration of intervention.

